## 12 STATISTICAL ANALYSIS

### 12.1 Sample Size

A total of 94 patients will be enrolled into this trial over an 18-month period (48 children and 46 adults). It is estimated that 6 to 8 clinical centers (12-16 patients per center) will be required to enroll sufficient patients in this period.

Initially, subjects were randomized to one of three treatment groups: placebo, low dose arginine and high dose arginine. With this amendment, subjects are now only randomized to placebo and low dose arginine. Subjects will be stratified by age group (5-17 years,  $\geq 18$  years) and since there could be drastic differences between these groups, they will be analyzed separately. Thus, all sample size calculations will be for each of these two groups.

We have identified three measurements that are of primary interest: Nitric Oxide, Gardos Channel Activity, and erythrocyte density (MCHC  $>41$ ). We will measure our panel of investigative laboratory measures at various time points between baseline and sixteen weeks (up to eight timepoints). In order to avoid making more assumptions than necessary for our sample size calculations, we will use a simpler model that reflects a single timepoint. Specifically, we will use a one-way ANOVA with three groups (one for each treatment arm) modelling the change from baseline in each of our three measurements. We will additionally assume a two-sided alpha of 0.05. The hypothesis tested from this model will be any difference in mean change from baseline between the three treatment groups.

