The literature suggests that the average NOx level in stable sickle cell patients is 25.5, with a standard deviation of 2.2. We assume that both groups start out with this mean and that the placebo group maintains this level across the length of the study. Based on preliminary findings, we expect a minimum increase of 1.75 for the high dose in the mean change from baseline NOx and the low dose to have a related 1.375 increase. If we assume that the variance is equivalent for the pre and post measurements, we can calculate the variance of the difference as the sum of the pre and post variances minus twice the covariance between pre and post measurements. Thus, our variance estimate depends greatly on the correlation between the pre and post measurements. Assuming a range of correlations (0.3, 0.5, and 0.7), we can then estimate the sample size we will need to detect the differences of 1.375 and 1.75 at 80% and 90% power. (See table below.)

Total sample sizes (for each age group) by power and correlation for NOx assuming a 1:1:1 randomization.

		Power	
		80%	90%
Correlation	0.7	27	33
	0.5	42	54

	0.3	57	72
--	-----	----	----

Given that the goal of this trial is exploratory, not confirmatory, we do not need to achieve a significant value on any specific hypothesis test. Additionally, a much larger treatment effect is anticipated, potentially giving us more power. Thus, a reasonable sample size to achieve our goals and provide us with a reasonable estimate, with the potential to see a significant effect is in the range of 48 total subjects in each age group. With the elimination of one dose of Arginine, the sample size of 16 adults per remaining treatment group will be used.

Insufficient data is available in the literature at this time to sufficiently estimate the expected within subject variability (at steady state of SCD) for the Gardos Channel Activity and erythrocyte density (MCHC >41) as measured by Advia. Sample size calculations would therefore be based on unfounded assumptions and are therefore not provided.

Since the rate of dropout cannot be estimated at this time, completion of the study will be monitored and dropouts will be replaced as they occur. This should pose no problem due to the relatively short duration of the trial. All available data on dropouts will be used in the analyses.

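### Section 12.1: the NOx sample-size table does not follow from the effects stated beside it; it matches a high-dose change of 2.75, not 1.75, and the protocol does not show which is meant

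*Protocol*

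**What the plan says.** All of this is in Protocol section 12.1, Sample Size.

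- **Model:** "we will use a one-way ANOVA with three groups (one for each treatment arm) modelling the change from baseline in each of our three measurements". The test is of "any difference in mean change from baseline between the three treatment groups". On the error rate: "We will additionally assume a two-sided alpha of 0.05".
- **Variability:** NOx in stable patients "is 25.5, with a standard deviation of 2.2". The variance of the change is built from equal pre and post variances less twice their covariance, at correlations 0.3, 0.5 and 0.7.
- **Effects:** placebo does not change; "we expect a minimum increase of 1.75 for the high dose in the mean change from baseline" in NOx, and the low dose is given a related increase of 1.375.
- **Table:** introduced with "we can then estimate the sample size we will need to detect the differences of 1.375 and 1.75 at 80% and 90% power", at 1:1:1 allocation. Totals per age group for 80%/90% power are 27/33 (correlation 0.7), 42/54 (0.5) and 57/72 (0.3).
- **Chosen size:** in the range of 48 per age group. The reasons given are that the trial is exploratory and that a much larger effect is anticipated. After the amendment: "With the elimination of one dose of Arginine, the sample size of 16 adults per remaining treatment group will be used". Section 7.2 adds the 16 children and 14 adults already randomised to the high dose, which makes 48 children and 46 adults.

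Section 12.1 gives no calculation for the other two primary measures, so this table is the protocol's only sample-size calculation.

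**The concern.** Section 12.1 states every input that the table needs, so the table can be recomputed without assumptions. It does not come out: the stated effects need roughly twice the printed numbers. The high-dose value of 1.75 appears twice in the text, so nothing warns a reader that it and the table disagree.

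The chosen 48 lies above the printed 42 (80% power, correlation 0.5). A reader would take the design to have more than 80% power for the stated effects in that case. Whether it does depends entirely on which of the two figures is right. Section 12.4.2 gives as a goal accurate power calculations for a phase III trial, so the planning effect used here should be unambiguous.

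**Working it through.** **Inputs (section 12.1):** SD 2.2 before and after; correlation ρ = 0.7, 0.5, 0.3; alpha 0.05; three equal groups; overall F test; no inflation for dropout.

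**SD of the change** = √(2 × 2.2² × (1 − ρ)) = 1.704, 2.200 and 2.603.

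**Power:** noncentral F with 2 and 3(n − 1) degrees of freedom and λ = n × Σ(μᵢ − μ̄)² / SD², where n is the number per arm. The total is 3 × the smallest n that reaches the target.

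**Sums of squares**
- 0/1.375/1.75: μ̄ = 1.0417, Σ = 1.0851 + 0.1111 + 0.5017 = 1.6979
- 0/1.375/2.75: μ̄ = 1.375, Σ = 1.8906 + 0 + 1.8906 = 3.7813

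**Example, ρ = 0.5, 80% power (SD² = 4.84)**
- With 2.75: n = 13 gives 78.7%. n = 14 gives λ = 14 × 3.7813 / 4.84 = 10.94 and 82.0%. The total is 42, as printed.
- With 1.75: n = 28 gives 79.2% and n = 29 gives 80.8%. The total is 87.

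**All cells (totals for 80%/90% power)**

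| ρ | Printed | 0/1.375/1.75 | 0/1.375/2.75 |
|---|---|---|---|
| 0.7 | 27/33 | 54/69 | 27/33 |
| 0.5 | 42/54 | 87/114 | 42/54 |
| 0.3 | 57/72 | 120/156 | 57/72 |

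For the stated effects the required total is 2.00 (54/27) to 2.17 (156/72) times the printed one. At the printed totals their power is 46–47% in the 80% column and 57–58% in the 90% column.

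**How closely the table fixes the effect.** With the low dose held at 1.375, only high-dose changes of about 2.74 to 2.77 match all six cells. With the high dose at 2.75, low-dose values from 1.125 to 1.625 (in steps of 0.125) also match. The table therefore identifies the high-dose effect much better than the low-dose one. Moving the low dose between 0 and 1.75 cannot rescue 1.75: the most favourable placing (0/0/1.75 or 0/1.75/1.75) still needs 45/60, 72/96 and 99/132.

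**Other readings tried with 1.75; none reproduces the table**
- Alpha 0.10: 42/57, 69/93, 96/129
- Low dose at half of 1.75: 60/78, 96/126, 132/174
- Pairwise two-sample comparison for 1.75, times three arms: 45/60, 75/102, 105/141 two-sided; 36/51, 60/84, 84/114 one-sided
- Residual SD 2.2√(1 − ρ²): 48/60, 66/87, 81/102
- Factor 2 dropped from the variance (the nearest): 30/36, 45/60, 63/81, missing every cell by 3 to 9

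**Power at the chosen size, same model.** For unequal arms, λ = Σnᵢ(μᵢ − μ̄)² / SD² with μ̄ weighted by nᵢ. For example, at ρ = 0.5 and 16 per arm, λ = 16 × 1.6979 / 4.84 = 5.61, which gives 52.5%.

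| Comparison | ρ 0.7 | ρ 0.5 | ρ 0.3 |
|---|---|---|---|
| Three groups, 16 each, high dose 1.75 | 76% | 52% | 39% |
| Adults 16/16/14, high dose 1.75 | 74% | 51% | 38% |
| Three groups, 16 each, high dose 2.75 | 98% | 87% | 74% |
| Low dose vs placebo only, 1.375, 16 vs 16, t-test on change | 60% | 40% | 30% |

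The last row does not depend on the high-dose value.

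**The case against.** **The table may be right and the text wrong.** A reader might infer from the recomputation that the stated sample sizes are about half of what is needed. The documents do not support that. It follows only if 1.75 is the real planning effect. The exact match at 2.75 points at least as strongly to a wrong figure in the text: 2.75 is twice 1.375, just as 0.10 g/kg/day is twice 0.05. In that case nothing is undersized. Nor do the documents establish a typing error. They print 1.75 twice and never mention 2.75. This objection stands against the stronger reading and leaves the contradiction in place.

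**Section 12.1 claims no power for 48.** It calls the trial exploratory, says that no particular test needs to be significant, and expects a larger effect. Sections 12.3.3 and 12.4.2 call the analyses descriptive. This softens the consequence, and it would be conjecture to say that a null low-dose result will be misread. It does not make the table correct, because the table is offered as the numbers for the two stated differences.

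**The planned analysis is not this model.** The synopsis and sections 12.3.1 and 12.4.2 specify baseline-adjusted longitudinal mixed models. Even a single-timepoint baseline-adjusted comparison (residual SD 2.2√(1 − ρ²), one further degree of freedom lost) gives about 83%, 65% and 57% for 0/1.375/1.75 at 16 per arm, and about 67%, 51% and 43% for low dose against placebo. The power figures under working therefore belong to the protocol's simplified model and must be labelled so.

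**The pairwise power is a separate matter.** The amended protocol keeps a three-group analysis with the earlier high-dose patients, so a three-group calculation still fits its stated hypothesis. That is right: leaving out the pairwise figure is not an arithmetic error, and adding it is only useful.

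**Conclusion.** The point holds as a contradiction between text and table in section 12.1. The stated inputs give totals of 54/69, 87/114 and 120/156, and the printed totals belong to a high-dose change of about 2.75. No other part of the protocol reconciles them, and only the sponsor can say which was meant.

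The difference is material to what the design delivers. At 48 per age group and correlation 0.5, power under the planning model is about 52% on one reading and 87% on the other. These figures rest on section 12.1's own simplifications: one timepoint, unadjusted change, SD 2.2 at both times and equal arms. They are not the power of the planned mixed model. The finding does not show that the trial is too small.

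**What to change.** The sponsor states which high-dose effect the table was computed for.

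- **If 2.75:** correct both mentions of 1.75 in section 12.1 and leave the table as it is.
- **If 1.75:** replace the table with 54/69, 87/114 and 120/156, and restate what 48 children and 46 adults deliver (about 76%, 52% and 39% at 16 per arm; 74%, 51% and 38% at 16/16/14).

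In either case, it is useful to add one line with the power of low dose against placebo at 16 per arm for a difference of 1.375: about 60%, 40% and 30% by t-test on change, labelled as applying to the simplified single-timepoint model.

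The cost is a correction to the text or the table. Enrolment, endpoints and analysis stay as they are. If 1.75 is confirmed, the stated power becomes less favourable.

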## 12.2 Analysis Populations

Patients who receive any clinical trial material (any dose of arginine or placebo) will be included in the intent-to-treat analysis. All analyses will be performed on the intent-to-treat population.

## 12.3 Statistical Considerations

### 12.3.1 Covariates

Baseline laboratory measurements will be controlled when analyzing laboratory outcomes. Other covariates may be considered in the analysis of clinical, laboratory, pharmacokinetic, and safety outcomes as needed.

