Study Population: Male or female Hb SS patients age 5 or more years Major Inclusion Criteria: History of at least one pain event in last 12 months Major Exclusion Criteria: Major organ dysfunction, treatment with hydroxyurea or transfusion within 3 months, history of recent priapism or retinopathy, pregnancy.
Sample Size: 94 (grouped into 48 children and 46 adults)
Randomization: One dose of arginine hydrochloride will be evaluated in this trial. Patients in each age group (children and adult) will be treated with one dose of arginine (0.05 g/kg/day) or placebo divided for BID dosing. Sixteen patients will be randomized to each dose level and placebo. Randomization will be stratified by center to preserve balance across treatment groups.
Data Analyses: Within each age group, we will evaluate differences in laboratory measures among the 3 groups (1 arginine group, one placebo group, and the previously collected arginine dose group) using random effects analysis of covariance techniques. Here the change in laboratory measures over each measurement time will act as the dependent variable of interest and the treatment status as the grouping factor. The baseline value of the laboratory measure and the time of the measurement visit will act as the fixed effect covariates and each patient

**Title of the Protocol:** Arginine Supplementation in Sickle Cell Anemia: Physiological and Prophylactic Effects  
will have a random intercept. Additionally, each laboratory measurement will be summarized by age group (pediatric and adult), treatment arm, and measurement time. No interim analyses are planned for this study. The SDCC will be responsible for data management and analysis.

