# These cardiac enzyme tests need to be done for all subjects who present with chest pain or any event that could be indicative of a cardiac event..

### 7.2.3 Research Laboratory Assessment

Patients will have ongoing assessment for both primary and secondary outcomes throughout the course of the study. Whenever possible, these assessments will be made when the patient is in the steady state and not in the midst of a complication due to sickle cell disease. The schedule for assessing research lab outcomes is outlined in the table below:

Test	Wk -4	Wk -2	Study Entry	Wk 1	Wk 2	Wk 4	Wk 8	Wk 12	Wk 14	Wk 16
Free Radical Biology										
Nitrotyrosine	X	X	X	X	X	X	X	X		X
8-iso-PGF2α	X	X	X	X	X	X	X	X		X
Endothelial Function										
ET-1	X	X	X	X		X	X	X		X
sVCAM-1	X	X	X	X		X	X	X		X
Erythrocyte Characterization										
Advia	X	X	X	X	X	X	X	X	X	X
Ektacytometry	X	X	X	X	X	X	X	X	X	X
Gardos Channel	X	X	X	X	X	X	X	X	X	X
Fetal Hemoglobin	X	X	X			X	X	X		X

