##### 9.5.2 Visit Two

At Visit 2 (Week -2, Study Day -14), blood will be collected for the two central labs as in Visit 1. Female patients of childbearing potential will receive a pregnancy test. Medical information will be collected including hospitalization and pain information, concomitant medication information, and AE information. The discontinuation criteria will be checked to make sure that the patient is still eligible for the study.

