##### 9.5.3 Visit Three Randomization

At Visit 3 (Week 0, Study Day 0), the Baseline/Study Entry Visit, blood will be drawn for both the central and local labs in the same manner that it was collected during Visit 1. A urinalysis will be performed and female patients of childbearing potential will receive

a pregnancy test. All patients will receive an echocardiogram. Hospitalization, pain, concomitant medication, and AE information will be collected. For all patients presenting with chest pain or cardiac events, an EKG will be done and CPK isoenzymes and troponin levels will be measured. The study coordinator will double-check the discontinuation criteria prior to randomizing the patient and distributing enough of the study drug for one month.

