### *12.4.2 Efficacy*

The goal of this study is to obtain laboratory and clinical information to justify a phase III clinical trial and to provide data to generate accurate power calculations for a subsequent phase III clinical trial. The two age groups (children and adults) will be analyzed separately to assess for differences in response to arginine therapy.

The laboratory variables NO, Gardos Channel activity, sickle red cell density (% of cells >41, as measured by Advia) are of primary interest. Additionally, sVCAM, H3 Technicon, Nitrotyrosine, 8-iso-PGF2 $\alpha$ , Ektacytometry, ET-1, and ECHO will be measured and analyzed as secondary efficacy variables. Since the goal of this protocol is to gain insight into the effect of arginine on multiple physiologic measures (e.g. erythrocyte characterization, endothelial function and free radical biology), we will model the change from baseline for all of the collected measurements over time using random effects longitudinal mixed models, with treatment and baseline measurement as fixed effects. This class of model allows us to control for the correlation induced by having multiple measurements on an individual. We will focus on estimating the relationship between each of the laboratory measures and treatment group over time.

Additionally, by judiciously choosing the structure of the fixed effects over time, we can investigate non-linear dose relationships as well.

Each laboratory measurement will be summarized by age group (pediatric and adult), treatment arm, and measurement time.

Clinical efficacy is a secondary endpoint for this trial. Clinical efficacy data will be collected on all patients. Specifically, patients will be asked for information on emergency room visits and hospitalizations, clinic visits for pain, and pain medication use. All clinical efficacy measurements will be summarized by age group, treatment arm, and measurement time (where applicable). Treatment differences may be examined using appropriate methods as the data permits.

All efficacy data will be analyzed descriptively to provide information for future trials. All analyses will be performed on the intent-to-treat population. Model assumptions will be confirmed and if broken, appropriate methods will be investigated.

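### Each primary endpoint is measured three times before treatment, but the model has one baseline value, apparently the study-entry value; using all three would probably sharpen the comparison

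*Protocol*

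**What the plan says.** The schedules in sections 7.2.2 (NOx) and 7.2.3 (Gardos channel, Advia) mark all three primary endpoints at Week -4, Week -2 and study entry. The Gardos row, for example, begins "Gardos Channel X X X". The visit descriptions agree: at Visit 2 "blood will be collected for the two central labs as in Visit 1".

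Section 12.3.1 states: "Baseline laboratory measurements will be controlled when analyzing laboratory outcomes". The Synopsis gives the model: "The baseline value of the laboratory measure and the time of the measurement visit will act as the fixed effect covariates", and each patient "will have a random intercept". Section 12.4.2 describes "random effects longitudinal mixed models, with treatment and baseline measurement as fixed effects", with change from baseline as the outcome. Baseline is therefore both a covariate and the reference for the change score, and each model description has one such term.

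The analysis variable is not defined. Two places point to study entry. Section 9.5.3 describes Visit 3 as "the Baseline/Study Entry Visit, blood will be drawn for both the central and local labs". Section 12.1 counts at most eight timepoints from baseline to Week 16, which fits study entry plus Weeks 1, 2, 4, 8, 12, 14 and 16.

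**The concern.** If baseline is the study-entry value alone, two of the three pre-treatment values of each primary endpoint are collected and then left out of the treatment comparison. A single draw carries the full visit-to-visit noise of the assay and the patient. Section 12.1 itself says that the variance of the change depends heavily on how strongly the pre- and post-treatment values correlate. Averaging several pre-treatment draws normally raises that correlation. With 16 patients per arm in each age group, precision matters, and here it would come from samples already scheduled.

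**Working it through.** **Inputs from the protocol.** Three pre-treatment draws (7.2.2, 7.2.3). Five on-drug visits: Weeks 1, 2, 4, 8 and 12. NOx SD 2.2, low-dose effect 1.375, pre-post correlation ρ of 0.3, 0.5 or 0.7, two-sided alpha 0.05, 16 per remaining arm (12.1). Random intercept (Synopsis), which implies the same correlation at every lag.

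**The plan's own figure.** The protocol states no precision gain for this choice, so there is none to reproduce. The NOx sample-size table in 12.1 is a separate matter. Its stated means (0, 1.375, 1.75) give 54/69, 87/114 and 120/156 for ρ = 0.7, 0.5 and 0.3, not 27/33, 42/54 and 57/72. That does not affect the percentages below, which depend only on ρ and the number of measurements.

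**Formula.** With b baseline draws averaged and m follow-up visits averaged, the baseline-adjusted variance, in units of SD², is

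V(b, m) = [1 + (m−1)ρ]/m − bρ²/[1 + (b−1)ρ].

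For ρ = 0.5 and m = 5: the first term is (1 + 2)/5 = 0.600. One baseline removes 0.25, leaving 0.350. Three baselines remove 3 × 0.25/2 = 0.375, leaving 0.225. The reduction is 1 − 0.225/0.350 = 35.7%.

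| ρ | Five-visit mean, 1 → 3 baselines | Reduction | Single visit, 1 → 3 baselines | Reduction |
|---|---|---|---|---|
| 0.3 | 0.350 → 0.271 | 22.5% | 0.910 → 0.831 | 8.7% |
| 0.5 | 0.350 → 0.225 | 35.7% | 0.750 → 0.625 | 16.7% |
| 0.7 | 0.270 → 0.148 | 45.4% | 0.510 → 0.388 | 24.0% |

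A simulation of the five-visit case at 16 per arm gave 22.8%, 35.0% and 44.9%.

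**Power for 1.375, two arms of 16, complete data**, using SD = 2.2√V and the noncentral t distribution:

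- Five-visit mean: 82 → 91%, 82 → 95% and 91 → 99% for ρ = 0.3, 0.5 and 0.7.
- Single-visit ANCOVA: 43 → 47%, 51 → 58% and 67 → 78%.

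**Sizing model of 12.1.** This is a single-visit change score without a baseline covariate. Its variance goes from 2(1−ρ) to 1 + (1+2ρ)/3 − 2ρ = 4(1−ρ)/3, one third lower at any ρ. Both model descriptions include a baseline covariate, so this is not the planned analysis.

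**If correlation fades with time (my assumptions; the protocol gives no correlation by lag).**

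- Partial decay, with 70% of the correlation stable and 30% decaying as exp(−weeks/4): the mean of three lowers variance by 14 to 24% over five visits and by 5 to 11% at Week 12.
- Pure first-order autoregression, with correlation 0.3 to 0.7 at four weeks: the mean of three raises variance by 16 to 27% over five visits.
- Study-entry value and screening mean as two separate covariates: no loss under pure autoregression, apart from one degree of freedom. Under equal correlation or partial decay, the gain is at least that of the simple mean.

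**The case against.** The strongest objection is that deriving baseline from repeated pre-dose values is ordinary SAP business, and that the protocol is not wrong. Adjusting for a study-entry value is valid and unbiased, and a mean of three draws is also one baseline value. Much of this stands. A reader might infer that the protocol excludes the screening values, but no section says so; study entry is only the natural reading. The point survives because the protocol already fixes the form of the model and labels the baseline visit, and following it as it reads leaves two collected values unused.

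Three stronger readings are also tempting, and the documents do not support them.

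- **A cost-free gain of 20 to 45%.** The size depends on equal correlation at all lags and on averaging over five visits. Fading correlation shrinks the gain and, in the purely autoregressive case, reverses it for the simple mean.
- **The same gain for every primary endpoint.** The 0.3 to 0.7 range is given for NOx only. Section 12.1 says within-subject variability cannot be adequately estimated for Gardos activity or density.
- **A rescue from low power.** Power of 30 to 60% for the low-dose comparison belongs to the single-visit unadjusted change score. The 22 to 45% gain belongs to the five-visit adjusted analysis, where power with one baseline is already 82 to 91%. The two do not occur together.

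The trial is also exploratory, and its analyses are declared descriptive, so this concerns efficiency and not validity.

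**Conclusion.** The point holds as a worthwhile improvement in efficiency. Three pre-treatment values exist for each primary endpoint, the model has one baseline term, and the text indicates that it is the study-entry value without excluding the other two. For NOx under the protocol's correlations and its random-intercept structure, using all three cuts the variance of the treatment effect by about 22 to 45% for the five-visit on-drug average and about 9 to 24% for a single-visit ANCOVA. These figures assume complete data and equal correlation over time. The direction of the gain from a simple mean is likely but not guaranteed. For Gardos activity and density, its size is unknown.

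**What to change.** In sections 12.3.1 and 12.4.2, adopt one of two definitions:

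1. Baseline is the mean of the available Week -4, -2 and 0 values. Use it both for the change score and as the covariate (mixing two baselines would change the gain), and add a sensitivity analysis with the study-entry value.
2. Keep the study-entry value as baseline, and enter the mean of the two screening values as a second covariate. This is the safer choice if correlation may fade with time, and it costs one degree of freedom in each age-group model.

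Either way, state that a missing screening draw is handled by using the values available, and align the Synopsis. The cost is a few sentences; no visit, blood draw or assay is added. The choice should be fixed before unblinded efficacy data are seen.
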